If body weight loss is greater than 10%, diuresis is monitored weighing the diaper and haematological examinations are performed. In this case, it is counselled an artificial milk integration after breastfeeding. Discharge can be influenced from the results of the controls and must be executed for the security of the newborn (9).

Health care providers must not be underestimated the possible allergies to formula milk and the mothers that give up breastfeeding after the use of formula milk. The newborn should receive breastfeeding from the delivery room (10,11). It is good practice, when the milk secretion is enough, to attach the infant to a single breast for each feeding and let it suck for 15-20 minutes (12). Quantity of milk that newborn assume for each feeding is object of careful evaluation. Double weighing consists in weighing newborn before and after feeding: the body weight difference is the quantity of milk assumed. In the first day of life, newborn should suck 10 gr of colostrum or milk for each feeding. Then starting from the second day of life, the quantity of milk assumed must be increased of 10 gr/die for the first week.

RegioneLombardia

Versione 3.0 del 30/07/2018

According to scientific revisions, salivary cortisol is a valid method for measuring adrenocortical activity in newborns because it is non-invasive in fact the measurement of salivary cortisol has been used as a stress marker in newborns since 1992 (13,14). The mechanism by which cortisol induces stress, concerns the hypothalamic-pituitary-adrenal axis. The hypothalamus produces the corticotropin-releasing hormone, which stimulates the production of adrenocorticotropin by hypophysis. Adrenocorticotropin induces the secretion of glucocorticoids such as cortisol by stimulating the cortex of the adrenal gland. An appropriate release of cortisol due to stress factor is vital for surviving and the loss of this mechanism increase the risk of morbidity and mortality for newborns. However, prolonged exposure to a high level of cortisol may increase the risk of cognitive and behavioural disorders, hypertension, hyperlipidaemia, insulin resistance, immune deficiency and hippocampal impairment (15,16). The separation from the mother, the exposure to painful procedures but also routine interventions such as physical examination, diaper changes and bathing increase the salivary cortisol level of the newborn compared to the basal state (17). The measurement of salivary cortisol in the newborn therefore has the aim of understanding and preventing those stressful conditions that may have long-term side effects. For this reason, the lose weight in the first days and double weighing should be a stress practice for the newborn.

2. Objective

Evaluation of salivary cortisol level as stress marker in newborns with body weight loss of $3 \pm 1,5\%$ at 24 hr from birth subjected to double weighing or to body weight control at 36 hr and 48 hr of life. Furthermore, evaluation of body weight trend between newborns subjected to double weighing or to body weight control at 36 hr and 48 hr of life.

3. Study Location

U.O. Neonatology, Department of mother and child's health, Poliambulanza Foundation, Brescia.

4. Population

Group A (Case): Newborns subjected to double weighing before and after breastfeeding, with body weight loss $>3\pm 1,5\%$ at 24 hrs or 6% at 48 hrs from birth

Group B (Control): Newborns with body weight loss $>3\pm 1,5\%$ at 24 hrs and 6% at 48 hrs from birth and subjected to weight control at 36 hr and 48 hr of life

5. Inclusion Criteria

- Gestational age: 37-42 wks
- Body Weight: >2500 g
- Body weight loss $>3\pm 1,5\%$ at 24 hr from birth
- First-born
- Eutocic delivery
- Mother BMI:19-24
- Glycaemia >50 mg/dl

6. Exclusion criteria

- Mother disease
- Admission in NICU
- Neonatal pathologies
- Utilization of human milk
- Body weight loss $> 10\%$

7. Procedure

Body weight of newborns will be collected at birth(T0), at 24 hr of life (T1) and at 48 hr of life (T2) by Eura Mod.AS/1 OMIP, Milano.

Group A will be subjected to double weighing, before and after the next 6 breastfeeding. Breastfeeding will be carried out each 4 hr.

Versione 3.0 del 30/07/2018

Group B will be subjected to monitoring of body weight only at 24, 36 hr and 48 hr of life.

Saliva sample of the newborns will be collected in oral cavity at 48 hr of life. Samples collected will be storage at -80 C for up to 4 months and analysed by analysis laboratory of Poliambulanza Foundation.

Measurement

Weight scale used to obtain body weight is Eura Mod.AS/1 OMIP, Milano.

Data collected will be reported on a database by Microsoft Office Excel 2016.

SalivaBio Infant's Swab (SIS) is the kit used to collect salivary cortisol.

Statistical analysis will be carried out by IBM SPSS Statistics for Windows, v.25 (Armonk,NY:IBM Corp.)

8.Primary Outcome

Evaluation of salivary cortisol levels at 48 hr of life after the practice of double weighing to analyse stress levels of the newborns

H0: There is not difference in salivary cortisol level between group A and B.

H1: Salivary cortisol level in group A is greater than group B.

9.Secondary Outcome

Evaluation of body weight increase between group A and B.

H0: There is not difference in the body weight increase between group A and B

H1: Group A shows a greater body weight increase than group B

10.Sample Size

[figure not shown]
Primary outcome will be evaluated by independent two samples t-test. Sample size will be computed setting:

Alfa error: 0.05

Beta error: 0.90

Effect size: 0.8

Sample size will be of 56 patients (28 group A + 28 group B)

Secondary outcome will be analysed by independent two samples t-test. Trend of body weight will be computed evaluating percentage increase from birth to 48 hr of life.

11. Randomization

Patients will be enrolled to group A or B by statistical software.

12. Reference

- 1) Janet M. Rennie, "Textbook of Neonatology" Elsevier Health Sciences, London, 2012.
- 2) Rodríguez G, Ventura P, Samper M P, Moreno L, Sarría A, Pérez-González J M.

Versione 3.0 del 30/07/2018

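### Section 4 gives the two randomised arms different weight-loss conditions, one set on the 48 h outcome itself; with 6% read as more than 6%, applying it biases the secondary comparison towards its alternative

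*Combined protocol and SAP*

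**What the plan says.** Section 4 (Population) describes each arm separately. Group A has a weight loss above the stated limit "at 24 hrs or 6% at 48 hrs from birth". Group B has a loss above the same limit "at 24 hrs and 6% at 48 hrs from birth and subjected to weight control at 36 hr and 48 hr of life". The first joins the two conditions with *or*, the second with *and*.

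Section 5 (Inclusion Criteria) has one condition for all newborns: "Body weight loss $>3\pm 1,5\%$ at 24 hr from birth". Section 2 (Objective) also has no 48 h condition and refers to "newborns with body weight loss of $3 \pm 1,5\%$ at 24 hr from birth". Section 11 assigns newborns to the groups by statistical software.

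Section 7 (Procedure) has Group A weighed "before and after the next 6 breastfeeding. Breastfeeding will be carried out each 4 hr". The secondary outcome is defined at the end of Section 10: "Trend of body weight will be computed evaluating percentage increase from birth to 48 hr of life". Its alternative hypothesis, in Section 9, is directional: "H1: Group A shows a greater body weight increase than group B".

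**The concern.** Randomised arms should share one eligibility rule, settled before allocation. Section 4 departs from this in three ways:

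- **The rule differs by arm.** Meeting the 48 h condition is compulsory only in Group B.
- **It acts after allocation.** Six feeds at 4 h intervals take 6 × 4 = 24 h, so double weighing runs from about 24 h to 48 h of life. A 48 h loss is known only when that period is over.
- **It is set on the outcome.** Loss from birth to 48 h is the secondary outcome with the sign changed.

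If the inequality sign is carried over to the 6%, Group B newborns with small losses are removed and Group A can keep theirs. Group A then shows the better weight course even if double weighing does nothing, which is what the secondary alternative asserts.

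The primary cortisol comparison is affected only if 48 h weight loss and cortisol are correlated. The background suggests that they may be: "the lose weight in the first days and double weighing should be a stress practice for the newborn".

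**Working it through.** **1. The plan's own sample size.** With an effect size of 0.8, 28 per group, alpha 0.05 one-sided and the printed 0.90 read as power, the noncentrality is 0.8 × √(28/2) = 2.99. The critical value on 54 degrees of freedom is 1.674, and power is 90.5%. The stated 56 is reproduced. A two-sided test would need 34 per group, so one-sided 0.05 is used below.

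**2. Assumptions.** The documents give no distribution of weight loss, so these inputs are illustrative:

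- 24 h loss: mean 4%, SD 1.5
- 48 h loss: mean 5, 6 or 7%, SD 2
- joint distribution bivariate normal, correlation 0.6
- 48 h losses above 10% removed in both arms
- no treatment effect, 28 per group

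Group B meets the 24 h rule and has a 48 h loss above 6%. Group A is read in two ways: the 24 h rule only (Section 5 also applies to it), or literally, either condition. The 24 h rule is itself unclear, so limits of 1.5, 3 and 4.5% and a range of 1.5 to 4.5% were tried.

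**3. Secondary outcome: simulated rate at which a one-sided t-test falsely favours Group A.** Each cell gives results for a mean 48 h loss of 5 / 6 / 7%.

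| 24 h rule | A: 24 h rule only | A: either condition |
|---|---|---|
| above 1.5% | 100 / 98 / 76% | 100 / 98 / 76% |
| above 3% | 100 / 92 / 53–55% | 100 / 92 / 57% |
| above 4.5% | 96 / 62 / 25% | 93 / 63 / 48% |
| 1.5 to 4.5% | 100 / 100 / 92% | 100 / 84 / 41% |

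At the 3% limit, with Group A on the 24 h rule, Group B's mean 48 h loss is 0.6 to 1.8 points larger, and 20 to 61% of Group B newborns who meet the 24 h rule fail the 48 h condition. With the 24 h/48 h correlation varied from 0.3 to 0.8, the range is about 10 to 100%.

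**4. A second set of assumptions.** Mean losses at 24 h/48 h of 3/5, 4/6 or 5/7%; SD 1.5 at 24 h and 1.5 or 2 at 48 h; correlation 0.5 to 0.9; limits 1.5, 3 and 4.5%.

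- Section 4 taken literally: Group B's loss is 0.28 to 1.96 points larger; false rejection 29 to 100%.
- Section 5 also imposed on both arms: 0.07 to 1.99 points larger; false rejection 8 to 100%.

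A hand check of one case (means 4/6%, 48 h SD 2, correlation 0.5, 3% limit, Section 5 imposed): the difference is 1.21 points, or 0.85 SD. Then 0.85 × √14 = 3.18, 3.18 − 1.674 = 1.51, and Φ(1.51) = 0.93. The simulation gave 0.94.

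**5. Controls.** With one common 24 h rule, false rejection is about 4 to 6%. Adding only the exclusion of losses above 10% at 48 h in both arms gives 4.3 to 5.2%, so that exclusion is not the cause.

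**6. Primary outcome.** If cortisol is uncorrelated with 48 h loss, power at 0.8 is 90 to 91% and the one-sided error 4.4 to 5.5%. At an assumed correlation of 0.3, power is 49 to 88% and the error 0.1 to 3.4%. Selection raises cortisol in Group B, which masks an excess in Group A.

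**The case against.** The strongest reply is that Section 5 is the operative list, Section 4 merely labels the groups, and *or* against *and* is a drafting slip. No available section describes removing or replacing Group B newborns with small 48 h losses. A newborn who first qualified for Group A at 48 h could not complete six double-weighed feeds before the 48 h saliva sample. A slip is therefore plausible, and under Section 5 alone there is no bias. But the available text gives no order of precedence, and Section 4 is the only place that defines each arm's population. Part of the background is missing from the text available for review, so an explanation there cannot be ruled out.

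Other points that stand:

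- The 6% carries no inequality sign of its own. Carrying over the preceding one is the natural reading; as a ceiling for Group B, it would reverse the direction. The condition would still be arm-specific, post-allocation and on the outcome.
- Under the literal *or*, Group A too is partly selected on 48 h loss. The exact statement is that only Group B is required to meet the 48 h condition.
- The sidedness of the secondary test is not stated. With a two-sided 0.05 test and Group A on the 24 h rule, the lowest case at correlation 0.6 falls from about 24% to 15%. At correlation 0.8, with a 4.5% limit and mean 7%, it falls from 9% to 5%, against a nominal 2.5% in that direction.
- The demonstrated bias concerns a secondary outcome in a document headed as a pilot study, and the primary effect rests on an assumed correlation.

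**Conclusion.** The concern holds. Section 4 contradicts Sections 2 and 5, and as written it places a post-allocation condition on the secondary outcome that is compulsory in one arm only. With 6% read as more than 6%, the bias favours the secondary alternative in every scenario examined. Its size depends on the assumed distributions: false-positive rates run from about 8% to 100%, against about 5% under a common rule. The primary comparison keeps its error rate and power unless cortisol correlates with weight loss; a positive correlation would cost power and would not inflate the one-sided error. The contradiction needs to be resolved because one of the two available readings invalidates a prespecified comparison.

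**What to change.** 1. Remove the 48 h conditions from Section 4, or state that they are criteria for neither entry nor retention. Both groups then share one weight-loss rule, assessed at 24 h before allocation.
2. State that all randomised newborns are analysed in the group to which they were allocated.
3. Reconcile the two forms of the 24 h rule. Section 2 reads as a range, while the sign in Sections 4 and 5 could mean a limit of 1.5, 3 or 4.5%. Use identical wording in all three sections; the choice is the sponsor's.
4. Separately, since it does not cause the bias above, state when the exclusion for losses above 10% in Section 6 applies, and keep newborns who cross it after allocation in the analysis. Their clinical handling is for the sponsor.

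The cost is a few lines of protocol text. The sample size of 56 and the study procedures do not change.

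### The primary cortisol t-test is valid, but it leaves unused a baseline recorded on every infant (percent weight loss from birth to 24 hr); prespecifying it as a covariate is a cheap gain in precision and robustness

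*Combined protocol and SAP*

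**What the plan says.** Section 10 gives the whole primary analysis in one sentence: "Primary outcome will be evaluated by independent two samples t-test". No covariate, regression model or sensitivity analysis appears there or elsewhere. The sample size inputs are "Alfa error: 0.05", "Beta error: 0.90" and "Effect size: 0.8", and the result is "Sample size will be of 56 patients (28 group A + 28 group B". Section 8 states a directional alternative: "H1: Salivary cortisol level in group A is greater than group B".

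On the candidate covariate:

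- Section 7 (Procedure): "Body weight of newborns will be collected at birth(T0), at 24 hr of life (T1) and at 48 hr of life (T2". Each infant therefore has a percent loss from birth to 24 hr, and Section 5 makes that loss an inclusion criterion.
- Section 7 applies double weighing to the six feeds that follow, one every 4 hr, which is roughly 24 to 48 hr of life. Saliva is taken only at 48 hr, so there is no baseline cortisol.
- The background, just before Section 2, says: "For this reason, the lose weight in the first days and double weighing should be a stress practice for the newborn".
- Section 11 is one sentence assigning infants by statistical software. It states no stratification or minimisation.

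**The concern.** The background puts early weight loss beside double weighing as a possible source of stress. Of the variables recorded before the intervention, 24 hr percent loss is the one the plan itself connects to the primary outcome. Neither the allocation nor the analysis makes use of it.

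Two things are at stake. If 24 hr loss predicts 48 hr cortisol, adjusting for it narrows the confidence interval without another infant or sample. And with 28 per group, the groups may by chance differ in 24 hr loss. A reader who sees such a difference in the baseline table will ask how much of the cortisol difference it explains. An adjustment chosen after seeing the data would be open to challenge; a prespecified one would not.

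**Working it through.** **Inputs from the documents.** Alpha 0.05, standardised difference d = 0.8, n = 28 per group (Section 10); direction A > B (Section 8). The printed beta of 0.90 is read as power, since only that reading gives the stated total.

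**Input not in the documents.** rho, the within-group correlation between 24 hr percent loss and 48 hr cortisol. It is an assumption, shown from 0 to 0.5.

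**Step 1: the plan's own figure.** Two-sample t-test, 54 df, noncentrality d·√(n/2) = 0.8·√14 = 2.993. One-sided at 0.05, power is 0.905 at 28 per group and 0.895 at 27. So 28 is the smallest n reaching 0.90, and the stated 56 is reproduced. Two-sided, power at 28 is 0.836 and 34 per group would be needed. The stated size therefore implies a one-sided test, although Section 10 does not say so.

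**Step 2: power with the covariate.** Adjustment multiplies the residual variance by (1 − rho²), uses one more degree of freedom (53 df), and inflates the variance by about 1 + 1/52 for estimating the slope. The effective standardised difference is d* = 0.8 / √[(1 − rho²)(1 + 1/52)].

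| rho | d* | adjusted power, one-sided | change from 0.905 |
|---|---|---|---|
| 0 | 0.792 | 0.900 | −0.005 |
| 0.1 | 0.796 | 0.903 | −0.002 |
| 0.2 | 0.809 | 0.910 | +0.005 |
| 0.3 | 0.831 | 0.923 | +0.018 |
| 0.4 | 0.865 | 0.939 | +0.034 |
| 0.5 | 0.915 | 0.959 | +0.054 |

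Break-even is at rho of about 0.14. Simulation with 40,000 trials at rho 0, 0.3 and 0.5 gave 0.900, 0.922 and 0.957. If the test were run two-sided, the same formula takes power from 0.836 to 0.862 at rho 0.3 and to 0.919 at rho 0.5.

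**Step 3: chance imbalance.** With simple 1:1 allocation, the difference in mean 24 hr loss has SD √(2/28) = 0.267 covariate SDs and a 95% range of ±1.96 × 0.267 = ±0.52. For a roughly normal difference, the chance of exceeding 0.25 SD in either direction is 35%, and of exceeding 0.5 SD is 6%.

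The resulting shift in the unadjusted cortisol difference is rho × imbalance. At rho 0.3:

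- mean absolute shift: 0.3 × 0.267 × √(2/π) = 0.064 SD, and 0.064/0.8 = 8% of the target;
- at the 95% limit: 0.3 × 0.52 = 0.16 SD, and 0.157/0.8 = 20% of the target.

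**Step 4: error rate.** Averaged over all randomizations, the simulated one-sided false-positive rate of the t-test was 5.0% to 5.1%. Among the roughly 3% of randomizations where group A has over 0.5 SD more loss, it was about 16% at rho 0.3 and 27% at rho 0.5. The adjusted analysis gave about 4% and 6% in the same subsets.

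**The case against.** The strongest reply is that nothing is broken. A t-test between randomized groups needs no covariates: its 5% level and confidence interval already allow for chance imbalance in 24 hr loss and in everything else, and planned power is met. That stands. A reader might infer that the unadjusted comparison is biased or confounded by weight loss. The documents do not support that; the excess error in Step 4 is conditional on an unlucky allocation and averages out.

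A reader might also infer that adjustment raises power. It does so only above rho of about 0.14, and nothing in the documents places rho there. Eligibility may pull it down. Section 2 describes a loss of 3 ± 1.5% at 24 hr, and Section 6 excludes losses above 10%. If the first is a window of 1.5% to 4.5%, then under an assumed uniform spread the SD is 3/√12 = 0.87 percentage points, and a 0.52 SD imbalance is about 0.45 points of body weight. Sections 4 and 5 print the criterion with a greater-than sign, so its meaning is unclear, but a narrow range would weaken the correlation.

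Nor is the 20% shift a maximum or a typical value. It pairs an assumed rho with a 95% limit, and 0.16 SD is about 0.6 of the comparison's own standard error (0.157/0.267).

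The link to stress is thin: one uncited sentence about the first days of life, not 24 hr loss specifically. It justifies choosing this covariate but does not establish that weight loss drives cortisol.

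Finally, baseline status is inferred. The 24 hr criterion and the following six feeds imply allocation at or after 24 hr, but no time is stated. Section 4 also joins the 24 hr loss to a 6% loss at 48 hr, with *or* for group A and *and* for group B. Applied literally, those definitions could create a systematic group difference in loss that a 24 hr covariate would not fully repair.

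**Conclusion.** The point holds as a modest, inexpensive improvement, and does not correct an invalid or underpowered test. The size of the gain is unknown because rho is unknown: a loss of up to 0.5 points of power below rho of about 0.14, a gain of about 2 points at 0.3 and about 5 at 0.5. Protection against chance imbalance is worth about 8% of the target effect on average at rho 0.3, and more in an unlucky allocation.

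These figures assume a one-sided test at 0.05, a linear relation between 24 hr loss and cortisol with the same slope in both groups, roughly normal residuals, 28 analysable infants per group, and allocation after the 24 hr weight and before double weighing. The last is essential: without it, 24 hr loss is not a true baseline.

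**What to change.** In Section 10, replace the sentence on the primary analysis with text such as:

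*The primary comparison will be a linear model of 48 hr salivary cortisol on group, with percent weight loss from birth to 24 hr as a continuous, prespecified covariate. The adjusted group difference with its confidence interval is the primary result. The unadjusted two-sample t-test will be reported as supportive.*

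In Section 11, state that allocation takes place once the 24 hr weight is recorded and before any double weighing. State the sidedness of the test in Section 10. Keep 28 + 28. Do not use the 36 hr or 48 hr weights as covariates, because they are measured after the intervention starts and may be affected by it. Reconcile the group definitions in Section 4 with each other and with the inclusion criterion in Section 5, so that eligibility is clearly settled before allocation.

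The cost is a few sentences and one extra term in the planned SPSS analysis. No further infants, samples or measurements are needed. The statistical price is one degree of freedom, at most about 0.5 points of power (0.905 to 0.900) if the covariate turns out to be unrelated to cortisol.

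### The secondary weight comparison leaves out the 24 h weight the trial already collects; a prespecified ANCOVA would probably be more precise, by an unknown amount

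*Combined protocol and SAP*

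**What the plan says.** All points are in the combined protocol and SAP.

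- **Outcome and test (Section 10).** "Trend of body weight will be computed evaluating percentage increase from birth to 48 hr of life", and "Secondary outcome will be analysed by independent two samples t-test". No covariate is named.
- **Hypothesis (Section 9).** It is directional: "H1: Group A shows a greater body weight increase than group B".
- **Weights (Section 7).** All infants are weighed at birth, 24 h and 48 h. For the control arm: "Group B will be subjected to monitoring of body weight only at 24, 36 hr and 48 hr of life".
- **Intervention (Section 7).** "Group A will be subjected to double weighing, before and after the next 6 breastfeeding", with the interval given as "Breastfeeding will be carried out each 4 hr".
- **Entry (Sections 2 and 5).** Both use weight loss at 24 h, so every enrolled infant must have that weight. Section 2 writes the rule as a band around 3%; Section 5 puts a greater-than sign before the same band.
- **Allocation (Section 11).** "Patients will be enrolled to group A or B by statistical software". No time of randomisation is given.
- **Group definitions (Section 4).** Group A is described by the 24 h criterion *or* a 6% figure at 48 h, Group B by the 24 h criterion *and* that figure.

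**The concern.** The change from birth to 48 h is the sum of the change up to 24 h and the change after it. If double weighing starts only after the 24 h weight, it cannot have affected the first part. The infant-to-infant spread in that part is then background noise in the group comparison, and it has been measured in everyone. An unadjusted t-test leaves the noise in; a regression on group and 24 h change removes whatever part of it predicts the 48 h value.

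At stake is the width of the confidence interval for the weight difference. The sample size was set on cortisol and no power is claimed for weight, so the precision of the weight result depends on how well the collected data are used. The covariate should be named in advance, so that it is not chosen after seeing the results.

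**Working it through.** **1. The plan's own figure.** Section 10 gives alpha 0.05, effect size 0.8 and 28 + 28 = 56. Its beta of 0.90 has to be read as power 0.90. A one-sided two-sample t-test (noncentral t) then needs 28 per group, with power 0.905, so 56 is reproduced. A two-sided test would need 34 per group (68). The figure concerns cortisol, and adjusting the weight analysis does not change it.

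**2. Timing of the 24 h weight.** Six feeds × 4 h = 24 h. Counted from the 24 h entry weight, this runs to about 48 h, when the outcome is measured. The 24 h weight therefore looks pre-intervention. This is inferred, since no randomisation time is stated.

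**3. Precision.** Let r be the within-group correlation between percent change at 24 h and at 48 h among enrolled infants. With N = 56, the ANCOVA variance relative to the t-test is (1 − r²) × (1 + 1/(N − 4)) = (1 − r²) × 53/52. The interval-width ratio is about its square root:

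| r | Width ratio | Effect on interval |
|---|---|---|
| 0 | 1.01 | 1% wider |
| 0.14 | 1.00 | equal |
| 0.2 | 0.99 | 1% narrower |
| 0.4 | 0.93 | 7% narrower |
| 0.6 | 0.81 | 19% narrower |
| 0.8 | 0.61 | 39% narrower |

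Break-even: (1 − r²) × 53/52 = 1 gives r² = 1/53, so r = 0.14. No SD or effect size is needed.

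**4. Is r likely to exceed 0.14?** Write the 48 h change as D1 + D2, with SDs s1 and s2 and correlation c. Then r = (s1 + c·s2) / sqrt(s1² + s2² + 2c·s1·s2). This is zero only when c·s2 = −s1, meaning that any extra first-day loss is on average fully regained by 48 h. As an assumed illustration, take 24 h loss uniform over 1.5–4.5%, so s1 = sqrt(9/12) = 0.87:

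| s2 | c | r | Variance ratio |
|---|---|---|---|
| 1.0 | 0 | 0.65 | 0.58 |
| 1.5 | 0 | 0.50 | 0.76 |
| 2.0 | 0 | 0.40 | 0.86 |
| 1.5 | −0.5 | 0.09 | 1.01 |
| 2.0 | −0.5 | −0.08 | 1.01 |

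A gain is probable, but strong catch-up removes it.

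**5. Power, under assumptions.** None of these values is in the documents: 24 h loss mean 4%, SD 1.5; 48 h loss mean 6%, SD 2; 28 per group; one-sided 0.05; 40,000 simulated trials per setting. Because the entry rule can be read in several ways, four readings were run. Gain in power (percentage points) for a true difference of 1 point of percent weight change, by correlation before selection:

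| Entry (24 h loss) | 0 | 0.3 | 0.5 | 0.7 | 0.85 |
|---|---|---|---|---|---|
| >3% | −0.6 | 1.2 | 5.6 | 14.1 | 23.1 |
| 1.5–4.5% | −0.8 | 0.2 | 2.4 | 7.4 | 12.0 |
| >4.5% | −0.6 | 0.3 | 2.6 | 8.2 | 12.6 |
| >1.5% | −0.7 | 2.3 | 8.0 | 20.6 | 33.3 |

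For correlations 0.3 to 0.85 across the four readings, the gain is 0 to 28 points at a 0.5-point difference and 0 to 7 at a 1.6-point difference. Type I error under random allocation was 0.049–0.052 for both methods.

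Entry selection weakens the correlation: 0.85 before selection becomes 0.76, 0.64, 0.66 and 0.82 among enrolled infants (rows in table order). The width ratios there are 0.65, 0.77, 0.76 and 0.57, in line with step 3.

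**6. If Section 4 is applied literally.** Group A was formed by the 24 h rule or loss above 6% at 48 h, and Group B by both, with no true difference and correlations 0.3–0.85. The 6% is read here as more than 6%. For entry >3%, the nominal 5% test rejects in 76–91% of trials with the t-test and 51–88% with ANCOVA. Across the four readings the ranges are 48–97% and 7–98%. Neither method is valid in that case.

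**The case against.** The strongest reply is that nothing here is wrong. Under randomisation the t-test is unbiased, the study is a pilot, weight is secondary and unpowered, and a simple valid test is a legitimate choice. The benefit depends on two unstated conditions and on a correlation nobody has supplied. A range from nothing to 33 power points does not tell the sponsor whether the gain matters. All of that stands, and it is why this is an inexpensive improvement rather than a correction.

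Three narrower points also stand in part:

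- **Selection lowers r.** With the assumed SDs and independent changes, r before selection is 1.5/2 = 0.75. Among enrolled infants it falls to about 0.64 (>3%), 0.51 (1.5–4.5%), 0.53 (>4.5%) or 0.71 (>1.5%). All are well above 0.14. At 0.3 before selection, however, the two tightest readings leave r of only 0.16–0.17 and practically no gain.
- **The SDs are single assumed values.** The power table would change with others. The width formula in step 3 would not.
- **Section 6 excludes weight loss above 10% without a time point.** Applied up to 48 h, this truncates the outcome. At correlation 0.85 it cuts the narrowing from 35% to 30% (entry >3%) and from 24% to 16% (entry >4.5%). The gain shrinks but remains.

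The Section 4 wording is a separate design problem. It appears here only because it decides whether any weight analysis is interpretable.

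**Conclusion.** The point holds as a modest efficiency gain on a secondary outcome. The planned t-test is not an error. ANCOVA on the 24 h change would narrow the interval once r among enrolled infants exceeds 0.14, which is probable because the covariate is a component of the outcome. The size is unknown, since the documents give no SD, correlation or effect size for weight. The downside is small: an interval about 1% wider and under 1 point of power if r is zero.

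The conclusion rests on two conditions: that randomisation follows the 24 h weight, and that infants are not selected on 48 h weight, whether through the Section 4 definitions or the undated 10% exclusion. The textual facts are firm; the size of the gain is not.

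**What to change.** Do the following in order.

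1. Reconcile the Group A *or* and Group B *and* definitions in Section 4, and say at what time the 10% exclusion in Section 6 applies.
2. State in Section 11 when randomisation takes place, so that the 24 h weight is confirmed as pre-intervention.
3. Keep the outcome and replace the secondary test in Section 10 with wording such as: *Percent weight change from birth to 48 h will be compared by ANCOVA (linear regression) on group, with percent weight change from birth to 24 h as the single covariate; the adjusted difference and its confidence interval will be reported.*

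If the 24 h weight proves to be post-randomisation, leave it out of the model.

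The analysis change costs one sentence and one degree of freedom. It needs no new data and leaves the sample size of 56 as it is.
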